5.3 Duration of Therapy

In the absence of treatment delays due to adverse events, treatment may continue for 1 year or 12 cycles (28 days per cycle) after transplant or until one of the following criteria applies:

- Disease Progression
- Intercurrent illness that prevents further administration of treatment
- Unacceptable adverse event(s)
- Evidence of PCP pneumonia or CMV viremia, confirmed at 2 consecutive blood draws at least 1 day apart with any value ≥ 500 IU/mL in plasma or evidence of documented CMV disease.
- Patient decides to withdraw from the study
- General or specific changes in the patient's condition render the patient unacceptable for further treatment in the judgment of the investigator.

5.4 Duration of Follow-up

Patients will be followed for 24 months after end of study treatment or until death, whichever occurs first. Patients removed from study for unacceptable adverse events will be followed until resolution or stabilization of the adverse event.

5.5 Criteria for Removal from Study

Patients will be removed from study at the time of disease progression as determined by protocol section 8.4. Exclusions are made for relapse isolated to the CNS which is able to be managed through local therapy.

6. REQUIRED DATA/STUDY CALENDAR

Pre-Study Testing Intervals

To be completed within 16 DAYS before study treatment:

- All blood work
- History and physical

To be completed within 28 DAYS before study treatment:

- Any X-ray, scan of any type (e.g., CT or MRI) or ultrasound that is utilized for tumor measurement

To be completed within 42 DAYS before study treatment:

- Any X-ray, scan of any type (e.g., CT or MRI) or ultrasound that is not utilized for tumor measurement
- Bone marrow biopsy and aspirate (unilateral) is required if there washistory of bone marrow involvement.

	Prior to Treatment	Cycle 1 Day 1	Cycle 1 Day 8 ± 3 days	Cycle 1 Day 15 ± 3 days	Day 1 of Each Subsequent Cycle ± 3 days ^l	Cycle 2 Day 15 ± 3 days	Cycle 3 Day 15 ± 3 days	End of Treatment* * ± 3 days	Time of Restaging and Post-treatment Follow-up*, %
Tests & Observations									
History & Progress Note	X	X			X			X	X
Physical Examination	X	X			X			X	X ^j
Pulse, Blood Pressure	X	X			X			X	X
Height	X								
Weight	X	X			X			X	X
Performance Status	X	X			X			X	X
Drug Toxicity Assessment	X	X			X			X	
Solicited Abnormalities/AEs	X	X ^A			X ^A			X	
Laboratory Studies									
CBC, Diff, Platelets	X	X			X			X	X
Serum Creatinine, CrCl (est), BUN	X	X			X			X	X
Serum Electrolytes	X	X			X			X	X
AST, ALT, Alk Phos, Bilirubin	X	X		X	X ^A	X	X	X	X
Uric Acid, Phosphate, LDH	X	X			X			X	X
Blood CMV PCR	X	X			X			X	
Beta2-Microglobulin	X							X	

Serum or Urine BHCg	X ^B							X	
Thyroid Function Tests (T3,T4, TSH)	X ^E				X ^E			X	
Triglycerides	X ^I							X	
HIV~	X ^{C~}							X	
HBsAg~, Anti-HBc~Ab,HepC Ab~	X~							X	
ECG	X		X ^F					X	
Staging									
CT/MRI (chest/abd/pelvis) with Tumor Measurements	X							X	X ^D
CT Neck	X							X	X ^D
PET (or PET/CT)	X							X	X ^D
Bone Marrow Asp & Biopsy	X							X ^G	X ^G
Histologic Review	X							X ^K	
Correlative Samples	X ^H	X ^H						X ^H	X ^H

Table 1

* Restage every 3 cycles during treatment (i.e., cycles 3, 6, 9, 12, etc.), then every 3 months for 1 year, then every 6 months for another year.

** If off study prior to month 12 study treatment

% Starting at cycle 15 through cycle 24: Visit window +/- 4 weeks. Starting at cycle 27 through cycle 36: Visit window +/- 12 weeks.

^ Monitor ALT, AST, Alk Phos and bilirubin in all patients every 2 weeks (or 15 days) for the first 3 cycles of treatment, than every 4 weeks during subsequent cycles.

~ If done before the transplant, no need to repeat them.

A. Abnormalities/adverse events should be solicited, and severity graded, on day 1 of each cycle of treatment.

B. In women of childbearing potential (as defined in Section 3.1.7). A negative serum or urine HCG test is required within 14 days prior to study.

C. Patients with known HIV positivity are excluded.

D. CT, PET or PET/CT done PRN to follow measurable disease. Scan to be done with or without PET depending on the patient disease status.

- E. Thyroid function tests every 3 cycles while on treatment and at completion of protocol therapy(Prior to treatment, C3D1, C6D1, C9D1, C12D1).
- F. ECG on day 8 of cycle 1, and then as clinically indicated. The steady-state (day 8) ECG is a requirement of the FDA under the Alliance IND for Zydelig.
- G. Repeat bone marrow aspirate and biopsy to confirm CR only if involved at baseline. Also a bone marrow aspirate/biopsy will be done if suspicion of bone marrow involvement.
- H. See protocol 19.2 Time Points of appendix D Correlative Studies
- I. Triglycerides Day 1 of cycles 3, 6, 9, 12 and then every 3 months until month 24. Then again at months 24, 30, & 36.
- J. Physical Exam during follow-up.
- K. Only if there is progression, as judged by the Investigator

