7. DOSING DELAYS/DOSE MODIFICATIONS

Please refer to table 2 below.

Patients who experience a Grade 2 or 3 toxicity and recover to \leq Grade 1 (or to pretreatment baseline level of toxicity) may continue treatment at the next lower dose level (i.e., Dose level 2 down to dose level 1).

Once the dose has been reduced, patients must remain at the reduced dose for 28 days. Dose escalation may occur at the discretion of the investigator and may occur every 28 days. Patients may have their dose de-escalated from level 2 to level 1, three times before being removed from treatment.

Please note:

- There are no dose escalations above 150 mg BID
- There are no dose reductions below 100 mg BID

Table 2

Dose Modification Schedule	
Dose Level	Dose of Zydelig
Level 2 (starting dose)	150 mg PO BID
Level 1	100 mg PO BID

Table 3

Dose Modifications for Toxicities Due to Zydelig

Pneumonitis	Any symptomatic pneumonitis		
	Discontinue Zydelig in patients with any severity of symptomatic pneumonitis		
ALT/AST	>3.0-5.0 x ULN	>5-20 x ULN	>20 x ULN
	Decrease Zydelig to 100 mg BID and monitor weekly until ≤ 1 x ULN.	Withhold Zydelig. Monitor at least weekly until ALT/AST are ≤ 1 x ULN, then may resume Zydelig at 100 mg BID.	Discontinue Zydelig permanently.
Bilirubin	>1.5-3 x ULN	>3-10 x ULN	>10 x ULN

	Decrease Zydelig to 100 mg BID. Monitor at least weekly until ≤ 1 x ULN.	Withhold Zydelig. Monitor at least weekly until bilirubin is ≤ 1 x ULN, then may resume Zydelig at 100 mg BID.	Discontinue Zydelig permanently.
Diarrhea*	Moderate diarrhea	Severe diarrhea or hospitalization	Life-threatening diarrhea
	Decrease Zydelig to 100 mg BID. Monitor at least weekly until resolved.	Withhold Zydelig. Monitor at least weekly until resolved, then may resume Zydelig at 100 mg BID.	Discontinue Zydelig permanently.
Neutropenia[^]	ANC 1.0 to <1.5 Gi/L	ANC 0.5 to <1.0 Gi/L	ANC <0.5 Gi/L
	Maintain Zydelig dose.	Decrease Zydelig to 100 mg BID. Monitor ANC at least weekly.	Interrupt Zydelig. Monitor ANC at least weekly until ANC ≥ 0.5 Gi/L, then may resume Zydelig at 100 mg BID.
Thrombocytopenia	Platelets 50 to <75 Gi/L	Platelets 25 to <50 Gi/L	Platelets <25 Gi/L
	Maintain Zydelig dose.	Decrease Zydelig to 100 mg BID Monitor platelet counts at least weekly.	Interrupt Zydelig. Monitor platelet count at least weekly. May resume Zydelig at 100 mg BID when platelets ≥ 25 Gi/L.

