Fatal and/or serious hepatotoxicity occurred in 18% of patients treated with Zydelig monotherapy and 11% of patients treated with Zydelig in combination trials. Elevations in ALT or AST greater than 5 times the upper limit of normal have occurred. These findings were generally observed within the first 12 weeks of treatment and were reversible with dose interruption. After resumption of treatment at a lower dose, 26% of patients had recurrence of ALT and AST elevations. Discontinue Zydelig for recurrent hepatotoxicity. Avoid concurrent use of Zydelig with other drugs that may cause liver toxicity. Monitor ALT and AST in all patients every 2 weeks for the first 3 months of treatment, every 4 weeks for the next 3 months, then every 1 to 3 months thereafter. Monitor weekly for liver toxicity if the ALT or AST rises above 3 times the upper limit of normal until resolved. Withhold Zydelig if the ALT or AST is greater than 5 times the upper limit of normal, and continue to monitor AST, ALT and total bilirubin weekly until the abnormality is resolved.

Severe Diarrhea or Colitis

Severe diarrhea or colitis (Grade 3 or higher) occurred in 14% of patients treated with Zydelig monotherapy and 19% of patients treated with Zydelig in combination trials. Diarrhea can occur at any time. Avoid concurrent use of Zydelig and other drugs that cause diarrhea. Diarrhea due to Zydelig responds poorly to antimotility agents. Median time to resolution ranged between 1 week and 1 month across trials, following interruption of Zydelig therapy and in some instances, use of corticosteroids.

Pneumonitis

Fatal and serious pneumonitis occurred in patients treated with Zydelig. In randomized clinical trials of combination therapies, pneumonitis occurred in 4% of patients treated

with Zydelig compared to 1% on the comparator arms. Time to onset of pneumonitis ranged from <1 to 15 months. Patients taking Zydelig who present with pulmonary symptoms such as cough, dyspnea, hypoxia, interstitial infiltrates on a radiologic exam, or a decline by more than 5% in oxygen saturation should be evaluated for pneumonitis. If pneumonitis is suspected, interrupt Zydelig until the etiology of the pulmonary symptoms has been determined. Patients with pneumonitis thought to be caused by Zydelig have been treated with discontinuation of Zydelig and administration of corticosteroids.

Infections

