14.3 Stratification Factors

- Patients will be analyzed based on the indolent or aggressive type of NHL given that the two groups historically have different outcomes after AutoSCT.
- Patients will be analyzed based on average daily dose of Zydelig through the treatment duration to assess for dose dependence on progression rate.

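### Table 1 schedules no blood count at the day-15 liver draws of cycles 1-3, leaving nominally 28 days without a required count early after transplant

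*Combined protocol and SAP*

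**What the plan says.** Section 6, Table 1 marks "CBC, Diff, Platelets" before treatment, at C1D1, on day 1 of each subsequent cycle (±3 days), at end of treatment, and in the restaging and follow-up column. The cells for C1D8, C1D15, C2D15 and C3D15 are blank. The liver row is marked at all three day-15 visits, and its footnote says "Monitor ALT, AST, Alk Phos and bilirubin in all patients every 2 weeks (or 15 days) for the first 3 cycles of treatment". Section 10.5 gives the matching two-week rule for transaminases: "Monitor ALT and AST in all patients every 2 weeks for the first 3 months of treatment". For neutropenia the same section asks only for close monitoring of counts, without an interval.

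Table 3 in section 7 ties dosing to counts. At ANC 0.5 to <1.0 Gi/L the instruction is "Decrease Zydelig to 100 mg BID. Monitor ANC at least weekly", and platelets of 25 to <50 Gi/L are handled the same way. ANC <0.5 or platelets <25 Gi/L interrupts dosing. No extra count is triggered above ANC 1.0 or platelets 50.

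Restaging is every third cycle (3, 6, 9, 12). Its column carries a count, but the day within the cycle is not given.

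**The concern.** Table 3's hematologic rules can act only on a count that has been taken. If counts fall after an acceptable day 1 and no one orders an unscheduled test, the reduction or interruption waits for the next cycle. A dip that recovers before then is never recorded.

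This matters more here than in many maintenance trials. Patients start 30 to 120 days after transplant, with entry floors of ANC >500 and platelets >20,000 per mm³ (section 3.1.1). Section 10.5 reports grade 3-4 neutropenia in 25% on monotherapy. Toxicity is the primary objective, and section 14.1 undertakes to report all toxicities by type and grade. By the protocol's own table in section 9.2.1, grade 3-4 neutropenia (36/146 = 24.7%) is at least as common as grade 3-4 ALT elevation (27/146 = 18.5%), yet only the liver tests are scheduled every two weeks.

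**Working it through.** The plan states no figure for this point, so there is nothing to reproduce first. The check is of the schedule, then of what a denser schedule would catch.

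**Could other text require a mid-cycle count?** The Synopsis (continuous monitoring of toxicity and graft failure, standard post-transplant supportive care), section 9.4 (standard medical practice) and section 14.1 (continuous toxicity monitoring) name no count at any interval. Section 10.5 names none for counts. The restaging count can help only in cycles 3, 6, 9 and 12, so cycles 1 and 2 are uncovered whatever day restaging falls on.

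**Gap between required counts, acceptable day-1 values** (28-day cycles, ±3-day windows, C1D1 fixed):

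- Now: 28 + 3 = 31 days at most from C1D1; 28 + 3 + 3 = 34 days at most later.
- With day-15 counts: 14 + 3 = 17 days from C1D1; 14 + 3 + 3 = 20 days later in cycles 1-3.

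**Mean delay to the next count for a persistent episode** (onset uniform between counts, nominal dates, half the interval): 28/2 = 14 days now and 14/2 = 7 days with the change, in cycles 1-3. Over 12 cycles: 0.25 × 7 + 0.75 × 14 = 12.25 days, against 14 now.

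**Chance that a scheduled count meets an episode.** The documents give neither onset time nor duration of neutropenia, so both are assumptions. On nominal dates an episode of d days is met with probability d/28 now and min(1, d/14) with the change: 25/50/75/100% against 50/100/100/100% for d = 7/14/21/28. A simulation with visit days uniform on −3 to +3 (600,000 draws) gives the values below. The gain is multiplied by 34 × 0.25 = 8.5 expected patients with grade 3-4 neutropenia.

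| Onset | Schedule | 7 d | 14 d | 21 d | 28 d |
|---|---|---|---|---|---|
| Cycles 1-3 | now | 0.240 | 0.490 | 0.740 | 0.956 |
| Cycles 1-3 | with day 15 | 0.491 | 0.912 | 0.990 | 0.993 |
| | extra patients | 2.1 | 3.6 | 2.1 | 0.3 |
| Uniform, 12 cycles | now | 0.247 | 0.497 | 0.747 | 0.958 |
| Uniform, 12 cycles | with day 15 | 0.310 | 0.603 | 0.811 | 0.967 |
| | extra patients | 0.5 | 0.9 | 0.5 | 0.1 |

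For example, for 14-day episodes in cycles 1-3: (0.912 − 0.490) × 8.5 = 3.6.

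**If the restaging count already falls mid-cycle** (a count around day 15 of cycles 3, 6, 9 and 12 in both schedules), the gains become 1.6/2.5/1.4/0.2 with onset in cycles 1-3 and 0.4/0.6/0.4/0.1 with uniform onset.

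**Platelets.** Grade 3-4 is 9/146 in section 9.2.1: 34 × 9/146 = 2.1 patients expected, so the gain is at most about 2.1 × 0.42 = 0.9.

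**The case against.** A count on day 1 of each cycle is a coherent schedule that matches the per-cycle solicitation of adverse events, and the calendar is a minimum. Section 10.5's call for close monitoring, together with ordinary post-transplant care, would prompt some unscheduled counts, and every gain above assumes there are none. Patients who are low on day 1 go straight to weekly counts, yet the gain is applied to all 8.5 expected cases. The figure of 3.6 needs every episode to start in cycles 1-3 and to last 14 days; the documents give early onset only for hepatotoxicity. Only ANC <0.5 or platelets <25 stops dosing. For grade 4 neutropenia (34 × 16/146 = 3.7 patients) the gain is at most 3.7 × 0.42 = 1.6, or 3.7 × 0.106 = 0.4 with uniform onset. Table 3 prescribes no permanent discontinuation for either count, so the section 14 decision hardly moves. Cycles 4-12 keep their gaps.

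Most of this stands, and it limits the size of the point. It explains why the range runs from about zero, why the upper end should not be read as an expectation, and why this is not an error. It does not remove the gap: text that names no interval cannot be relied on to produce a count, and a trial that reports toxicity by grade should not depend on unscheduled testing that may differ between sites. The halving of the interval in cycles 1-3 needs no assumption about onset or duration.

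**Conclusion.** The concern holds as a design gap worth closing. In at least cycles 1 and 2, and in cycle 3 unless restaging falls mid-cycle, a patient with ANC ≥1.0 and platelets ≥50 Gi/L on day 1 has no required count until the next cycle.

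The benefit of closing it is modest: about 0 to 3.6 more patients with grade 3-4 neutropenia met by a scheduled count. This assumes that the 25% monotherapy rate carries over to the post-transplant setting, that no unscheduled counts are taken, and the onset patterns and 7- to 28-day durations shown. The main value is earlier action under Table 3 and a more complete toxicity record. Any effect on the proportion removed for toxicity is expected to be small.

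**What to change.** In Table 1, mark "CBC, Diff, Platelets" at the existing C1D15, C2D15 and C3D15 columns. Table 3, the solicited adverse-event schedule and cycles 4-12 stay as they are.

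The cost is at most 3 × 34 = 102 extra counts from venipunctures already scheduled, plus review of the results and the calendar wording. Three side effects should be accepted knowingly:

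- Somewhat more cytopenias will be recorded, so hematologic toxicity will look less favourable.
- There will be more reductions to 100 mg BID, and section 7 says "Once the dose has been reduced, patients must remain at the reduced dose for 28 days". One such period removes (300 − 200) × 28 = 2,800 mg of 300 × 336 = 100,800 mg (2.8%). That takes the 12-cycle average from 300 to 291.7 mg/day, which feeds the section 14.3 analysis: "Patients will be analyzed based on average daily dose of Zydelig through the treatment duration".
- Each reduction counts toward the section 7 limit: "Patients may have their dose de-escalated from level 2 to level 1, three times before being removed from treatment". On nominal dates a reduction at C1D15 (day 15) runs to day 43, which is C2D15, so the next one that a day-15 count could trigger is at C3D15 (day 71). The new counts alone can therefore supply at most two of the three, and only if the investigator re-escalates in between.

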3. Patients without evidence of documented disease progression clinically or radiographically (stable disease [SD], partial remission [PR] or complete remission [CR]) who have had count recovery (ANC > 500 cells/mm³, non-transfused platelet count > 20,000 K/mm³) and are at least 30 days post ASCT, but no more than 120 days post ASCT.

Exclusion Criteria:

1. Lack of engraftment
2. Patients with active lymphoma CNS disease

3. Patients with active infection defined as requiring systemic antibiotic treatment and fever within 48 hours of screening.
4. Patients with progressive disease, as defined in protocol section 8.4
5. Patients who progressed while previously taking Zydelig
6. Patients with moderate to severe lung disease including:
 - 6.1. Patients requiring O2 supplementation
 - 6.2. Patients unable to walk 50 feet without stopping to rest
 - 6.3. Moderate to severe obstructive or restrictive disease of the lung
7. Patients with inflammatory bowel disease
8. Patients with active hepatic disease, liver cirrhosis, or known HBV/HCV infection
9. Patients with de novo diffuse large B-cell lymphoma
10. Patients with h/o PCP or CMV infections

Intervention and Mode of Delivery:

Oral Zydelig at 150 mg twice daily continuously on 28-day cycles.

Dose delays/modifications as below for Grade 2 or above for some hematological and non-hematological toxicities such hepatotoxicity, diarrhea/colitis/intestinal perforation, pneumonitis, infections, neutropenia and thrombocytopenia, or any other grade 3 non-hematologic toxicity considered at least possibly related to Zydelig.

Duration of Intervention and Evaluation:

iNHL and tiNHL patients will be eligible after ASCT.

Start of therapy would occur after engraftment, minimum at day 30 post ASCT and no later than 120 days post-ASCT.

Patients will continue on Zydelig up to one year or to progression/relapse/death or unacceptable toxicity, whichever occurs first.

HDT/ASCT will occur as soon as possible based on successful mobilization, collection and infusion of bone marrow or peripheral blood stem cells at a minimum of 2×10^6 CD34+/Kg of weight.

Myeloablative transplant preparative regimen is based on institutional standards.

Engraftment will be defined as ANC over 500 cells/mm³ and non-transfused platelet count of 20K/mm³. Standard supportive care in the post-transplant setting will be given.

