1.2. Secondary Objectives

1.2.1. Assess the efficacy of Zydelig into the post- ASCT maintenance setting for iNHL and tiNHL immediately after ASCT.

The corresponding endpoint is to report the 1-year PFS after the transplantation. PFS is defined as time to progression, relapse of the disease or death. The efficacy endpoint would be improvement of 1-year PFS after ASCT by 20% based on an approximate baseline PFS of 60% for iNHL and tiNHL.^{1,2} The expected 1-year PFS will be around 80%.

Survival without progression or death will be determined using the Kaplan-Meier estimates at 1 year post ASCT.

1.2.2. 2-year PFS.

2-year PFS will be determined using the Kaplan-Meier estimates at 2 years post ASCT.

1.2.3. Non-relapse mortality (NRM).

NRM is defined as death in the absence of competing risks, relapse or progression of disease. This secondary endpoint will be characterized and presented as a cumulative incidence at 3 months and 12 months after SCT.

1.2.4. Overall survival (OS).

Survival without death will be determined and presented as Kaplan-Meier estimates at 1 and 2 years post ASCT.

1.2.5. Correlative studies.

See Appendix D.

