3. PATIENT SELECTION

3.1. Eligibility Criteria

3.1.1. Inclusion Criteria (must meet all)

1. Histologically documented (by HPI or pathology report) iNHL as defined by follicular lymphoma (FL), marginal zone lymphoma (MZL), lymphoplasmacytic lymphoma/Waldenstrom disease (LPL/WM) and small lymphocytic lymphoma (SLL) or tiNHL as defined by large B cell transformation of any of the above entities including chronic lymphocytic leukemia (CLL)
2. Patients must be eligible to undergo high dose chemotherapy (HDT) followed by ASCT as a form of remission consolidation
3. Patients without evidence of documented disease progression clinically or radiographically after ASCT (stable disease (SD), partial remission (PR) or complete remission (CR)) who have had count recovery (ANC > 500 cells/mm³, non-transfused platelet count > 20,000 K/mm³) and are at least 30 days post ASCT but no more than 120 days post ASCT

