14.4 Analysis of Secondary Endpoints

14.4.1 1-year PFS after ASCT.

PFS is defined as the time from the date of ASCT till progression or death whatever comes first. PFS function will be estimated using the Kaplan-Meier approach with 90% Confidence Interval.

Analysis of secondary objective(s):

The 1-year PFS will be estimated and reported using the Kaplan-Meier curve with the corresponding 90% confidence interval.

- 14.4.2 2-year PFS will be calculated with the same method as 1-year PFS (see 13.4.1).
- 14.4.3 Cumulative incidences of NRM at 3 months and 12 months by competing risks model and Grey's test.
- 14.4.4 The Cox regression model will be used to assess plausible risk factors for PFS and OS. The correlatives findings will be incorporated into time-to-event analyses using appropriate statistical models. Statistical analysis will be conducted by the BSS of the GCC.
- 14.4.5 Correlatives Studies
Please see Appendix C

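### Restaging is timed from first dose but PFS is read at exactly 1 and 2 years after transplant, with no scan tied to either date, so both estimates can be biased modestly upward

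*Combined protocol and SAP*

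**What the plan says.** **Imaging clock.** Section 6, Table 1 footnote: "Restage every 3 cycles during treatment (i.e., cycles 3, 6, 9, 12, etc.), then every 3 months for 1 year", followed by 6-monthly restaging for another year. Section 8 repeats this. Cycles are counted from the first dose. The same table sets a visit window after treatment: "Starting at cycle 15 through cycle 24: Visit window +/- 4 weeks". From cycle 27 to cycle 36 the window is 12 weeks either way.

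**Start of drug.** Section 3.1.1 admits patients who "are at least 30 days post ASCT but no more than 120 days post ASCT". The Synopsis agrees: "Start of therapy would occur after engraftment, minimum at day 30 post ASCT and no later than 120 days post-ASCT".

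**PFS clock.** Section 14.4.1: "PFS is defined as the time from the date of ASCT till progression or death whatever comes first". Section 1.2.1: "Survival without progression or death will be determined using the Kaplan-Meier estimates at 1 year post ASCT". Section 1.2.2 does the same at 2 years. Section 1.2.1 gives a baseline 1-year PFS of about 60% and an expected value of about 80%.

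**Treatment duration.** Section 5.3: "treatment may continue for 1 year or 12 cycles (28 days per cycle) after transplant". Synopsis: "Patients will continue on Zydelig up to one year or to progression/relapse/death or unacceptable toxicity, whichever occurs first", with no starting point named.

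No section ties a restaging to 12 or 24 months after ASCT, says what date a progression is given, or provides a landmark window or an interval-censored analysis.

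**The concern.** Start days span 90 days, and restagings during treatment are 84 days apart. Day 365 after ASCT can therefore fall anywhere between two restagings, depending only on when the patient began the drug. Suppose lymphoma progresses after the last restaging before day 365 and is first seen at the next one. If progression is dated at detection, the Kaplan-Meier estimate treats that patient as progression-free at 1 year. The same applies at day 730. The error can only raise PFS, more patients do not shrink it, and the confidence interval does not include it. At stake is the trial's main efficacy figure, 1-year PFS.

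**Working it through.** The plan states no power or precision for PFS, so there is no figure of its own to reproduce.

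**Inputs.** Start day S = 30 to 120 (Synopsis, Section 3.1.1); 28-day cycles (Section 5.3); restaging at cycles 3, 6, 9, 12 and onward (Section 6); landmarks at days 365 and 730; 1-year PFS of 60% or 80% (Section 1.2.1). Assumptions: all 91 start days equally likely, constant hazard, scans done on schedule, no drop-out.

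**Step 1: restaging days after ASCT.** The plan does not say whether restaging at a given cycle means its day 1 or its end, so both are shown.
- Day 1 of the cycle: S + 56, 140, 224, 308. Cycle 12 falls after day 365 when S > 57, which is 63 of 91 start days (69%).
- End of the cycle: S + 84, 168, 252, 336. Cycle 12 falls on day 30 + 336 = 366 at the earliest, so after day 365 for every patient.

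**Step 2: distance from day 365.**

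| | Day 1 reading | End-of-cycle reading |
|---|---|---|
| Restaging within 14 days | 29/91 = 32% | 36/91 = 40% |
| Within 28 days | 64/91 = 70% | 64/91 = 70% |
| Within 42 days | 91/91 | 91/91 |
| Mean days from last earlier restaging | 40 | 44-45 |
| Maximum | 83 | 83 |

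So 60-68% have none within 2 weeks, and all have one within 6 weeks.

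**Step 3: upper bound on the 1-year bias.** Patients must be progression-free to enter, so PFS is counted from S. If the last restaging by day 365 is on day L, and every event is found by scan and dated at detection:

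bias = exp[−λ(L − S)] − exp[−λ(365 − S)], with λ = −ln(0.60)/365 = 0.00140 or −ln(0.80)/365 = 0.00061 per day.

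Example (S = 60, day 1 reading): restagings fall on days 284 and 368. At the 60% hazard, exp(−0.00140 × 224) = 0.73 and exp(−0.00140 × 305) = 0.65, a bias of about 8 points. This is close to the worst start day.

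Averaged over S:
- 60% hazard: true 0.667, read as 0.706 (day 1) or 0.710 (end of cycle), about 4 points.
- 80% hazard: true 0.838, read as 0.859 or 0.861, about 2 points.

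If half of progression is found clinically, these become about 2 points and 1 point. On average 12-14% of progressions between first dose and day 365 are affected even in this worst case (0-31% by start day).

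**Step 4: 2 years.** The same formula at day 730, with follow-up restaging every 84 days or every calendar quarter, gives 2.3-2.7 points at the 60% hazard and 1.7-1.9 points at the 80% hazard. A simulated window of 4 weeks either way adds about 0.2 points. Cycle 27 day 1 is S + 728, so day 758 or later for everyone. A late visit there cannot worsen the day-730 estimate, and an early one can only reduce the bias.

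**Step 5: scale.** The 90% half-width at n = 34, ignoring censoring, is 1.645 × √(0.6 × 0.4/34) = 13.8 points and 1.645 × √(0.8 × 0.2/34) = 11.3 points.

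**The case against.** **Section 5.3 may already supply the scan.** If treatment ends 1 year after transplant, patients starting on days 30-120 stop after 335 to 245 days on drug. The end-of-treatment column of Table 1, with CT/MRI and PET within 3 days, would then fall near day 365 for those still on drug, and their 1-year bias would largely vanish. This is a fair reading of one sentence. It sits badly with the calendar, which schedules tests on day 1 of cycle 12, a visit that 69% of start days would not reach by day 365. It also does nothing for patients who stopped early, or at 2 years. The documents do not settle the point.

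**The bound is a worst case.** Deaths do not shift. Patients on drug are examined and have LDH measured on day 1 of every cycle, and footnote D allows imaging as needed, so some progression will be found between restagings. This stands, and it is why the figures are upper bounds. That footnote also means a restaging visit need not include a scan. This is a larger gap, but a separate one: the two clocks differ even if every scan is done.

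**Materiality.** PFS is secondary, is reported without a test, and the bias is well inside the confidence interval. Kaplan-Meier with detection dating is conventional. This limits the weight of the point but does not remove a known one-directional error.

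**Stronger readings that the documents do not support.** A reader might infer that most patients have no scan near 1 year, but 70% have one within 4 weeks. A reader might infer that progression before 1 year is generally dated after it, but only scan-detected progression after the last earlier restaging can be. A reader might think the 12-week window adds bias at 2 years; Step 4 shows it cannot. Nor can one conclude that the estimate is not comparable with the historical 60%. The documents give neither the scan schedule nor the dating rule behind that figure, and a similar bias there would partly cancel.

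**Conclusion.** The point holds as a modest one. The imaging and PFS clocks differ, no restaging is tied to either landmark, and no rule dates progression. The upward bias in 1-year PFS is at most about 4 points on average at the 60% hazard and 2 points at the 80% hazard, and about half that if half of progression is found clinically. At 2 years it is about 2 points. These sizes rest on evenly spread start days, a constant hazard, scans on schedule, detection dating, and treatment not being cut off at 1 year after transplant. Patients who stop early leave the cycle-based schedule, so their scan times cannot be derived. The size of any bias relative to the historical 60% is unknown. Starting the PFS clock at first dose would not solve the problem: cycle 12 ends on day 336 of that clock and the next restaging is at about day 420.

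**What to change.** 1. In Section 6, schedule the existing restaging nearest to 12 months, and the one nearest to 24 months, after ASCT at that landmark within 2 weeks either way. For that visit only, this replaces the 4-week (or 12-week) window. Adjust the adjacent restagings: a 42-day move would otherwise stretch an 84-day interval to 126 days.
2. Also, or instead if scans are not moved, add to Section 14.4 an interval-censored estimate of 1- and 2-year PFS beside the Kaplan-Meier estimate, using the dates of the last negative and first positive restaging. This handles scans shortly after the landmark without forcing those events to count before it. State how progression is dated in the Kaplan-Meier analysis.
3. Reconcile the Synopsis, Section 5.3 and the end-of-treatment footnote of Table 1 on when treatment ends relative to transplant, so that it is clear whether an end-of-treatment scan falls near day 365.

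**Cost.** Calendar and analysis wording, with no extra scan at 1 year because a restaging is always within 42 days. At 2 years the nearest one is at most 42-56 days away, depending on the reading. Scan intervals become somewhat uneven, and reported PFS may be a few points lower.
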